Subject Selection:	 Subjects or parents or legal guardian of the subject who are willing and able to sign consent Male and female subjects aged ≤18 years of age Infants, children and adolescents undergoing cardiopulmonary bypass for repair of a large unrestrictive VSD, an ostium primum ASD or a partial or complete AVSD Pre-operative echocardiogram which confirms the cardiovascular anatomy and defect to be surgically repaired Exclusion Criteria: Evidence of pulmonary artery or vein abnormalities on the pre-operative echocardiogram that will not be addressed surgically. Specific abnormalities excluded include the following: Significant pulmonary artery narrowing not amenable to surgical correction Previous pulmonary artery stent placement Significant left-sided atrioventricular (AV) valve regurgitation not amenable to surgical correction Pulmonary venous return abnormalities not amenable to surgical correction Pulmonary vein stenosis not amenable to surgical correction Preoperative requirement for mechanical ventilation or

11 August 2017	
	 intravenous inotrope support Presence of fixed or idiopathic pulmonary hypertension (i.e. Eisenmenger's Syndrome) prior to surgical repair Pre-operative use of medications to treat pulmonary hypertension Pregnancy; Sexually active females of child-bearing potential must be willing to practice an acceptable method of birth control for the duration of study participation (e.g. oral contraceptive, hormonal implant, intra-uterine device) Participation in another clinical trial within 30 days of Screening or while participating in the current study, including the 28 days of follow-up post study drug administration. Any condition which, in the opinion of the investigator, might interfere with the study objectives
Endpoints:	Primary Efficacy Endpoint:
	A composite variable consisting of the longer of either (1) length of time on mechanical ventilation or (2) length of inotrope use. The definition of mechanical ventilation shall include invasive and non-invasive mechanical ventilation including bilevel positive airway pressure (BPAP) or continuous positive airway pressure (CPAP).
	Secondary Efficacy Endpoints:
	Length of time on mechanical ventilation
	 Length of time on positive pressure ventilation
	 Length of time of inotrope use

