1.1.2 Pediatric CHD Patients

Children undergoing surgery for congenital heart defects are especially susceptible to developing CPB-induced acute lung injury due to age dependent differences in the inflammatory response, and the elevated sensitivity of their immature organ systems to injury as well as distinct differences between pediatric and adult CPB (Kozik and Twedell 2006). Neonates and infants are especially affected as the relatively large extracorporeal circuit size, the blood prime and the need for increased flow rates result in greater exposure of blood to the foreign surface (Schure AY et al. 2010).

For congenital cardiac surgery, the extracorporeal circuit must be adjusted to a wide range of age groups and size variations, from 1.5kg premature infants to >100kg adolescents or adults. Infants and children have smaller circulating blood volumes, higher oxygen consumption rates and, often, highly reactive pulmonary vascular beds. In addition, neonates and infants have labile thermoregulation and immature organ systems with multiple implications for ischemic tolerance and inflammatory response. Many complex repairs require a bloodless operative field, which can be difficult to achieve in the presence of intra or extra cardiac shunts, aortopulmonary collaterals, or otherwise increased pulmonary venous return (Schure AY et al. 2010).

With the possible exception of secundum ASD cases, in which recovery is relatively and consistently robust, there is so far, no known biomarker or patient characteristic among pediatric CHD patients linked with the probability of clinically significant CPB-induced ALI. It appears to occur in approximately 1/3 of pediatric CHD surgeries (Russell et al. 1998).

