4.3.2 Inclusion Criteria

To be eligible for study entry subjects must satisfy all of the following criteria:

- Subjects, parents, or legal guardian of the subject who are willing and able to sign informed consent
- Male and female subjects aged ≤18 years of age (females of child-bearing potential must be willing to practice an acceptable form of birth control; i.e. oral contraceptive, hormonal implant; etc.)
- Infants, children and adolescents undergoing CPB for repair of a large unrestrictive VSD, an ostium primum ASD, or a partial or complete AVSD
- Pre-operative echocardiogram which confirms the cardiovascular anatomy and defect to be surgically repaired

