5.1.1.2 Baseline Visit (Day of Surgery, Pre-operation)

The following evaluations will be performed on the day of surgery, prior to the operation:

- Body weight for calculating study drug dosage
- Inotrope and other concomitant medication documentation
- Urine pregnancy test for females of child-bearing potential
- Randomization
- Preparation of study drug by the hospital pharmacy
 - Blood draw (prior to surgery; in the operating room [OR], after induction of

anesthesia); for: plasma L-citrulline (1.0 mL)

Adverse events documentation (pre-treatment)

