For the total postoperative duration, the same analyses as described for the primary endpoint will be applied. Again, as sensitivity analyses subjects who died will (1) be excluded from analysis and (2) be assigned a length of time of chest tube placement of 28 days.

The total amount of chest tube drainage (mL), added up during each duration of chest tube as described above, will be summarized using descriptive measures and compared between groups using an ANOVA with a fixed effect for treatment group.

L-citrulline Plasma Levels

Summary statistics using descriptive measures will be tabulated for plasma L-citrulline levels.

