The total amount of chest tube drainage (mL), adding up each duration of chest tube as described above, will be summarized using descriptive measures and compared between groups using an ANOVA with a fixed effect for treatment group.

L-citrulline plasma levels

L-citrulline plasma levels will be obtained on each patient at set times. Individual concentration-time curves will be plotted to confirm that they are \geq the threshold level of 100 $\mu\text{mol/L}$. In addition, summary statistics using descriptive measures will be tabulated.

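### Chest tube drainage is compared in raw mL with no allowance for body size, which adds avoidable noise to an exploratory secondary comparison

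*SAP*

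**What the plan says.** SAP section 4.4.2 defines the volume part of thoracotomy output as "The total amount of chest tube drainage (mL), adding up each duration of chest tube as described above", to be "summarized using descriptive measures and compared between groups using an ANOVA with a fixed effect for treatment group". Protocol section 7.1.4 has the same variable, "The total amount of chest tube drainage (mL), added up during each duration of chest tube as described above", "compared between groups using an ANOVA with a fixed effect for treatment group"; the synopsis agrees. Neither document gives this variable a per-kg or body-surface scaling, a weight or age covariate, a log transformation, a rank test or an age stratum.

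The population is wide: "Male and female subjects aged ≤18 years of age", with no lower limit, and "Infants, children and adolescents undergoing CPB for repair of a large unrestrictive VSD, an ostium primum ASD, or a partial or complete AVSD". The background (Protocol 1.1.2) describes the field as ranging "from 1.5kg premature infants to >100kg adolescents or adults". Randomization is stratified by site only (Protocol 4.2 and 4.4.4).

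Weight is collected on the day of surgery: "Body weight for calculating study drug dosage". SAP section 4.2 tabulates it, and no efficacy model uses it.

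SAP section 4.4.2 tests secondary endpoints at 5% two-sided and labels them all exploratory.

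**The concern.** Drained volume can be expected to rise with the size of the child. If it does, a treatment-only ANOVA on mL puts the variation in size into the error term, although a baseline measurement that would remove much of it is already in the database. Neither the stratification nor the model balances or adjusts for weight.

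The plan allows for size or age elsewhere. Table 1 in Protocol 6.2.2.1 sets its bleeding threshold per kg per hour, the quantity closest to chest drainage. Arterial pressure limits are set by age (Protocol 5.1.2.2), and hemodynamic changes are adjusted for baseline (SAP 4.4.2). Chest tube duration, the other half of this endpoint, gets the Wilcoxon test through the primary-endpoint methods.

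At stake are the precision and readability of one listed secondary efficacy comparison.

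**Working it through.** **Arm size.** The only sample size in the documents is 92 per group, for the primary endpoint (SAP 1.3). Noether's formula reproduces it: p = Φ(0.6/√2) = 0.6643, so n = (2.576 + 1.282)² / [6 × (0.1643)²] = 91.85, rounded up to 92. It is used here only as the arm size. No mean, SD or expected effect is given for drainage, so every other input below is an assumption.

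**Model.** Volume = weight × drainage per kg, both lognormal, with log-SDs s_w and s_k. Then CV² of raw volume = exp(s_w² + s_k²) − 1, and CV² of mL/kg = exp(s_k²) − 1. Their ratio is approximately the factor by which the required sample size grows when raw mL is used. Weight's share of the log-variance is s_w²/(s_w² + s_k²).

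**Main setting.** Median weight 6 kg, s_k = 0.6, 25% less drainage per kg on drug, 92 per arm, 5% two-sided. CV² of mL/kg = exp(0.36) − 1 = 0.433. Powers for raw mL and mL/kg are simulated with two-sample t-tests, which equal a two-group ANOVA.

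| s_w | CV² of raw mL | N ratio | Weight share of log-variance | Power, raw mL | Power, mL/kg |
|---|---|---|---|---|---|
| 0.3 | 0.568 | 1.31 | 20% | 73% | 84% |
| 0.4 | 0.682 | 1.57 | 31% | 66% | 84% |
| 0.6 | 1.054 | 2.43 | 50% | 50% | 84% |
| 0.9 | 2.222 | 5.13 | 69% | 28% | 84% |

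For log mL/kg, the noncentrality is |ln 0.75| / (0.6 × √(2/92)) = 0.2877/0.0885 = 3.25, so power = Φ(3.25 − 1.96) = 90%. A Wilcoxon test on mL/kg has relative efficiency 3/π = 0.955 under this model, so power = Φ(3.25 × √0.955 − 1.96) = about 89%.

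**Other weight mixes.** 30% reduction, 4,000 simulated trials per setting, volume proportional to weight. Cells show power with raw mL vs mL/kg.

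| Assumed weights | s_k 0.5 | s_k 0.8 | s_k 1.0 |
|---|---|---|---|
| Mostly infants (CV 0.36) | 95 vs 99% | 63 vs 72% | 42 vs 49% |
| Young children (CV 0.53) | 85 vs 99% | 54 vs 73% | 37 vs 48% |
| 85% infants or toddlers, 15% at 15–60 kg (CV 1.06) | 46 vs 99% | 31 vs 74% | 23 vs 49% |
| Uniform 3–60 kg (CV 0.52) | 85 vs 99% | 55 vs 74% | 36 vs 49% |

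The loss runs from about 5 to 54 points, and required N grows 1.2 to 6.1 times.

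**Volume not proportional to weight.** Main setting, s_w = 0.4, 0.6 and 0.9. With volume ∝ weight^0.67, raw mL gives 75, 66 and 49% against 81, 80 and 75% for mL/kg. With weight^0.5, it is 79, 74 and 62% against 80, 74 and 60%, so the t-test on mL/kg gains nothing. Across the weight^0.5 settings tried, a rank test on mL/kg or an ANCOVA of log volume on log weight still did better than raw mL (37–90% against 28–81%).

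**No treatment effect.** Raw mL rejected in 3.4% to 5.6% of trials, with a mean ratio of about 1.00. Among null trials in which mean weight differed between arms by |t| > 1.5, rejection rose to about 12%, 15% and 21% for s_w = 0.4, 0.6 and 0.9. The overall rate stays near 5% because better-balanced trials reject less often.

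**The case against.** The strongest reply is that the loss may be small and matters little. Neither document gives trial weights or drainage values. The preceding study, CIT-002-01, enrolled 22 children aged 3 months to 5.5 years (Protocol 1.4); a similar intake would narrow the weight spread. The low end of the power range is also doubtful: median 6 kg with log-SD 0.9 puts Φ(ln 0.25/0.9) = 6.2% of children below 1.5 kg, the smallest size that the protocol quotes for the whole field. Exact proportionality favours mL/kg, and a larger per-kg spread hides weight: at s_k = 1.0 with a 25% reduction, power is 29% vs 35% (s_w 0.4) and 25% vs 34% (s_w 0.6). The analysis is exploratory, and the stated secondary objective is chest tube duration, not volume.

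All of this stands, and it limits the size of the point. It does not supply a reason to leave out a measured baseline variable when a suitably specified analysis did better in every setting tried.

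A reader might infer that body size swamps the comparison, that most of the variance is weight, or that a few adolescents will decide the result. The documents do not support this. In the main setting weight is a majority of the log-variance only at s_w = 0.9, and the number of large adolescents who will enroll is not given. A reader might also infer bias or false positives; randomization rules out the first, and null rejection stayed near 5%.

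**Conclusion.** The point holds as one of efficiency and interpretability. Raw mL with a treatment-only ANOVA carries avoidable noise from body size, and if the arms happen to differ in weight the planned analysis cannot separate that from a drug effect. Under the main assumptions the cost is roughly 11 power points (73% against 84%) at log-weight SD 0.3 and 56 points (28% against 84%) at 0.9. It is smaller when per-kg spread is large and, for a t-test on mL/kg, nil when volume rises with the square root of weight. These figures are illustrations, because no trial weights or drainage data are given. The primary endpoint, the sample size and the 1% test are unaffected.

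**What to change.** Before unblinding, amend SAP section 4.4.2 and list the change in section 5:

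- Compare total drainage per kg of Day 0 body weight by the Wilcoxon rank-sum test, with a Hodges-Lehmann 95% interval. State that subjects without a chest tube count as 0 mL. Section 4.4.2 sets only their duration to zero, and section 4.8 allows no imputation for volume. The rank test accommodates these zeros.
- As a supporting analysis, fit an ANCOVA of log volume on treatment and log weight in subjects with drainage above zero. This does not require volume to be proportional to weight.
- Keep raw mL as a descriptive summary.

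The data are already collected. The cost is SAP wording, a recorded deviation from the protocol's ANOVA and one extra table. Choosing the scale after unblinding would be open to challenge.

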4.5 Safety Analysis

Safety endpoints will be analyzed using the SAF.

Adverse events

Pre-treatment adverse events (PTAE) and treatment adverse events (TAE) will be analyzed separately. TAE are defined as all adverse events (AE) with time of onset or worsening on or after the time of first drug administration. If unclear due to incomplete start time / date of AE or drug administration, AEs will be assumed as TAEs.

Adverse events (AE) will be summarized by system organ class (SOC) and preferred term (PT) according to Medical Dictionary for Regulatory Activities (MedDRA) version 19.0. The number of events, as well as the number and rate of affected subjects will be reported for each treatment group. AEs will be summarized also by severity, and by relationship to study medication.

Separate analyses will be done for serious AEs and AEs leading to death.

Preferred terms of AEs with a proportion of $\geq 5\%$ in either L-citrulline or placebo group will be additionally tabulated in descending order of frequency together with the relative risk (RR), risk difference (RD), and Odds ratio (OR).

SAEs will additionally be tabulated by time of onset after time from the end of the surgery (variables "Date of surgery" and "End time" from section/CRF "Surgery"). The following timeframes will be used:

- ≤ 0 hours: Occurrence from time of first drug administration until and inclusive time of end of the surgery
- >0 to ≤ 12 hours: Occurrence after time of end of the surgery until and inclusive + 12 hours
- >12 to ≤ 24 hours: Occurrence after time of end of the surgery + 12 hours until and inclusive + 24 hours
- >24 to ≤ 36 hours: Occurrence after time of end of the surgery + 24 hours until and inclusive + 36 hours
- >36 to 48 hours: Occurrence after time of end of the surgery + 36 hours until and inclusive + 48 hours
- >48 hours: Occurrence after time of end of the surgery + 48 hours until

If unclear due to incomplete start time / date of AE or drug administration, AEs will be assigned to category >0 to ≤ 12 hours.

No statistical testing procedures will be applied to the analysis of AEs.

Incidence of refractory hypotension

Refractory hypotension is defined as dropping of mean arterial (blood) pressure below specific age-related criteria (see below) for more than 30 minutes. I.e., 2 or more successive mean arterial blood pressure (MAP) measurements within a time frame of at least 30 minutes have to be below the criteria as listed below.

The number of subjects with any refractory hypotension from end of surgery until 48 hours will be compared between groups using Fishers' exact test. Additionally, a logistic regression analysis will be applied including factors treatment and site.

Hypotension assessment (Refractory hypotension is defined as a 20% drop of MAP below specific age-related criteria (Haque and Zaritsky (2007) for greater than 30 minutes):

- Infants: MAP of 40
- Age 1 year: MAP of 40
- Age 2 years: MAP of 44
- Age 3 years: MAP of 47
- Age 4 years: MAP of 52
- Age 6 years: MAP of 53
- Age 7 years: MAP of 52
- Age 8 years: MAP of 54
- Age 9 years: MAP of 55
- Age 10 years: MAP of 56
- Age 11 years: MAP of 57
- Age 12 years: MAP of 58
- Age 13 years: MAP of 59
- Age 14 years: MAP of 61
- Age 15 years: MAP of 62
- Age 16 years: MAP of 63
- Age 17-18 years: MAP of 64

Laboratory values

Laboratory values will be analyzed descriptively. For quantitative parameters, absolute values as well as absolute and percentage changes from Baseline will be tabulated using summary statistics for all observed time points. For qualitative variables, frequency tables will be generated for all observed time points.

A conversion to the given standard units will be performed if necessary. Concentrations below the limit of quantification will be set to zero.

All laboratory values will be classified as normal or abnormal according to the laboratories normal ranges. Abnormal values will be indicated as clinically significant or not clinically significant by the investigator. Shift tables (normal / abnormal, not clinically significant / abnormal, clinically significant) will be created illustrating changes with respect to the laboratories normal ranges and clinical significance between Baseline and post Baseline visits Day 1, Day 2, and Day 28/ Discharge.

The following laboratory parameters were determined and will be described for the corresponding visits:

Hematology

Type of all parameters is quantitative.

- Hemoglobin
- Hematocrit
- Red blood cell (RBC) count
- White blood cell (WBC) count (total and differential)
- Platelet count

Serum Electrolytes, BUN, and creatinine

Type of all parameters is quantitative.

- Serum electrolytes (Na, K, Ca, Mg and Cl)
- BUN
- Creatinine

Liver function tests

Type of all parameters is quantitative.

- Bilirubin (total)
- AP
- AST
- ALT
- LDH

Coagulation

Type of all parameters is quantitative.

- ACT

Urinalysis

Specific gravity and pH are quantitative, the remaining parameters are qualitative.

- Visual: Color, Clarity/Turbidity
- Chemical: pH, specific gravity, glucose, ketones, nitrites
- Microscopic: RBCs, WBCs, epithelial cells, casts, bacteria

No statistical testing procedures will be applied to the analysis of laboratory values.

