 hospitalization may be considered a serious adverse event when, based upon
 appropriate medical judgment, it may jeopardize the subject and may require medical
 or surgical intervention to prevent one of the outcomes listed in this definition.

Documentation and Assessment of AE's and SAE's

Every adverse event, whether serious or not, must be recorded as soon as is reasonably possible in the patient's CRF. The following must be included:

- date of onset (or exacerbation in the case of worsening of an existing AE)
- frequency
- duration of effect

Additionally, the Principal Investigator (PI) must assess every adverse event in the CRF for severity and causality and must define the action taken (defined below).

Assessment of Severity (not to be confused with "seriousness")

Each AE/SAE will be assigned a category by the investigator as follows:

Mild An AE/SAE that is easily tolerated by the subject, causes minimal discomfort and does not interfere with everyday activities.

Moderate An AE/SAE that is sufficiently discomforting to interfere with normal

everyday activities; intervention may be needed.

Severe An AE/SAE that prevents normal everyday activities; treatment or other

intervention usually needed.

If there is a change in severity of an AE/SAE, it must be recorded as a separate event.

Assessment of Causality

Every effort will be made by the investigator to assess the relationship of the AE, if any, to the IMP. Causality should be assessed using the categories defined below:

Unrelated Clinical event where evidence exists that the symptom is definitely

related to etiology other than the study treatment (e.g., trauma secondary to a motor vehicle accident or a symptom suggestive of another illness which is not accepted to be a possible reaction to the

study treatment).

Unlikely Clinical event with a temporal relationship to IMP administration makes

a causal connection improbable, but that could reasonably be

explained by underlying disease or other drugs or chemicals.

Possible Clinical events with a reasonable temporal relationship to IMP

administration, but that could also be explained by concurrent disease or other drugs or chemicals that have a possible temporal relationship to the study treatment; however, a potential alternative etiology exists which may be responsible for the symptom (e.g., fever or irritability when other symptoms are present that suggest another etiology, for

example: upper respiratory infection).

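### SAP 4.5 sends serious adverse events of unclear onset time to the >0 to ≤12 h interval even when the recorded date rules that interval out

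*SAP*

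**What the plan says.** SAP 4.5 (Safety Analysis, Adverse events) adds a timing table: "SAEs will additionally be tabulated by time of onset after time from the end of the surgery". It has six categories: ≤0 h (from first study drug to the end of surgery), four 12-hour intervals up to 48 h, and >48 h. The first postoperative interval is defined as "Occurrence after time of end of the surgery until and inclusive + 12 hours" and the last closed one as "Occurrence after time of end of the surgery + 36 hours until and inclusive + 48 hours".

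The fallback rule opens with the condition that the category be unclear, and then gives the cause and the consequence: "incomplete start time / date of AE or drug administration, AEs will be assigned to category >0 to ≤ 12 hours". It sets no requirement that this category agree with whatever part of the onset is known.

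Three other statements bear on it:

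- Protocol 6.2.2.1 lists what must be recorded for every adverse event. For onset it asks for "date of onset (or exacerbation in the case of worsening of an existing AE"), alongside frequency and duration. It does not ask for a clock time.
- SAP 4.5 defines treatment adverse events as those "with time of onset or worsening on or after the time of first drug administration", which presumes that an onset time can be available.
- SAP 4.8 says that missing safety data are neither estimated nor imputed and that safety summaries rest on observed data.

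**The concern.** A rule for partial dates should use the part that is known. This one discards it: an SAE recorded on Day 2 with no time is plainly not in the first 12 hours after a Day 0 operation, yet the rule counts it there.

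The table exists to show when SAEs arise relative to surgery and to an infusion that runs for up to 48 hours. Adverse events receive no statistical testing, so timing is read directly from displays of this kind. If some SAEs from Days 1 and 2 have no clock time, the table would show them as early postoperative events although the source dates say otherwise. The rule is also a form of imputation, which does not fit SAP 4.8.

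**Working it through.** The plan gives no figure to reproduce, so the check compares each calendar day with the table's intervals.

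**Inputs**
- Intervals in hours after end of surgery (SAP 4.5): ≤0, (0,12], (12,24], (24,36], (36,48], >48.
- Assigned interval when unclear (SAP 4.5): (0,12].
- Assumption: surgery ends on Day 0, at clock hour *e*, with 0 ≤ *e* < 24. The documents give no typical end time, so all 1,440 possible minutes were enumerated; 14:00, 16:00 and 18:00 are illustrations.

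**Formula.** An SAE dated Day *d* with no time began between 24*d* − *e* and 24(*d* + 1) − *e* hours after the end of surgery. The rule applies if that span touches more than one interval. The assigned interval is possible only if the span overlaps (0,12].

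**Day 0.** The span runs from −*e* to 24 − *e*. It is unclear for 1,439 of 1,440 end times, and (0,12] is possible for all but one (23:59). An intra-operative event could still be placed after surgery, but the date does not exclude the interval.

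**Day 1.** The span runs from 24 − *e* to 48 − *e*.
- It is unclear for all 1,440 end times.
- Overlap with (0,12] needs 24 − *e* ≤ 12, that is *e* ≥ 12. For the 720 end times up to 11:59 the assigned interval is impossible.
- For *e* ≥ 12 the share of the day inside it is (*e* − 12)/24:
  - 14:00: 2/24 = 8%
  - 16:00: 4/24 = 17%
  - 18:00: 6/24 = 25%

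**Day 2.** The span runs from 48 − *e* to 72 − *e*. It is unclear for all 1,440 end times. Since *e* < 24, its start is always later than 24 h, so (0,12] is impossible in all 1,440.

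**Day 3 and later.** The span starts at 72 − *e* or later, which is always more than 48 h. Only >48 h is possible, so the category is never unclear and the rule does not apply.

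**Intervals compatible with the date, for a 14:00 end (shares of clock time)**

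| Recorded day | Hours after surgery | Compatible intervals | Assigned by the SAP |
|---|---|---|---|
| Day 1 | 10 to 34 | >0–12 (2/24 = 8%), >12–24 (12/24 = 50%), >24–36 (10/24 = 42%) | >0–12 |
| Day 2 | 34 to 58 | >24–36 (2/24 = 8%), >36–48 (12/24 = 50%), >48 (10/24 = 42%) | >0–12 |
| Day 3 | 58 to 82 | >48 only | rule not triggered |

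**The case against.** The strongest reply is that the rule is narrow and its consequences small. Much of that stands.

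- *Scope.* A reader might infer that every SAE with an incomplete time goes to the first 12 hours. The condition in the SAP sentence does not support that: a date-only SAE from Day 3 onward has only one possible category. The protocol collects SAEs up to 30 days after study drug, so most of the reporting window is untouched.
- *Frequency.* A reader might infer from the protocol's date-only list that all SAEs could lack a time. The documents do not show this. The SAP speaks of onset time and start time, which suggests that a time is collected, and the adverse event CRF page is not available. The protocol list is a minimum, not a CRF specification.
- *Percentages.* The 8% and 25% are shares of clock time. They would be shares of events only if onsets were spread evenly over the day, which nothing in the plan states.
- *Consequence.* A reader might infer that a late, infusion-related cluster would be hidden, or that moved events would pass for surgical complications. Neither is shown. The infusion starts 30 minutes after decannulation, so the first 12 hours are largely on infusion too. The same rule applies to both arms. SAE totals and the summaries by preferred term, severity and relationship do not use the interval.
- *Intent.* Keeping unclear events on treatment is consistent with the SAP's rule that adverse events of unclear timing count as treatment adverse events.

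None of this justifies overriding a known date. Treating a Day 2 event as a treatment adverse event does not require placing it within 12 hours of surgery.

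**Conclusion.** The point holds in a limited form. When triggered, the rule gives a certain error for every Day 2 SAE without a time, and for every Day 1 SAE without a time after surgery ending before 12:00. After a later end, the assigned interval is possible for Day 1 but covers only part of that day. Day 0 is normally compatible, and Day 3 onward is unaffected.

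This rests on surgery ending on Day 0 and on the record carrying a date without a usable time. The number of SAEs affected cannot be determined from the documents and could be small. The damage is confined to one supplementary, untested table, in which later SAEs would appear too early. SAE counts and the primary analysis do not change. It still merits correction, because the stated rule yields classifications that the source data contradict and one sentence removes the fault.

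**What to change.** In SAP 4.5, replace the default with:

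*If the onset time is incomplete, the recorded date is used. If the date is compatible with only one interval, the SAE is assigned to that interval; otherwise it is shown in a separate row, onset time unknown, by calendar day (Day 0, Day 1, Day 2, no date).*

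Reconcile this with the no-imputation statement for safety data in SAP 4.8.

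Defaulting to the earliest compatible interval would not be enough. A Day 1 SAE after an afternoon operation would still go to >0 to ≤12 h, and a Day 0 SAE would normally be moved to ≤0 h, so postoperative events would be counted as intra-operative.

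If the adverse event CRF has no onset-time field, also collect the clock time for SAEs with onset on Day 0 to Day 2.

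**Cost.** One SAP sentence and an extra row in one table, which is the small downside. The rule can be changed without unblinded data. The CRF field is needed only if it is absent; writing the requirement into Protocol 6.2.2.1 would mean a protocol amendment with ethics approval. If onset times prove complete, the change alters nothing.
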